9.2.2. Exclusion criteria

A patient who meets the following criterion is not eligible for inclusion:

• Concurrent enrolment in an interventional clinical trial involving either an investigational medicinal product or medical device

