9.1. Study design

This is a multinational, open-label, observational PASS that will evaluate the long-term safety and efficacy of avapritinib in the first line or following ≤ 4 months of imatinib treatment in at least 50 patients with PDGFRA D842V-mutated GIST. Three patient populations are planned to be enrolled:

- Patients with PDGFRA D842V-mutated GIST who are scheduled to receive avapritinib in the first-line (or have received imatinib for ≤4 months)
- Patients with PDGFRA D842V-mutated GIST who are already receiving treatment with avapritinib (in the first-line or following ≤ 4 months of imatinib treatment)
- Patients with PDGFRA D842V-mutated GIST who previously received treatment with avapritinib in the first line or following ≤4 months of imatinib treatment and have discontinued treatment

In addition to evaluating safety and efficacy of first-line avapritinib treatment, patients who were initially treated with imatinib for \leq 4 months are also being in included this study to allow for practical, real-world, clinical experience with use of avapritinib in the PDGFRA D842V-mutated GIST population setting and increase the feasibility of study completion in this ultra-rare patient population.

Informed consent will be obtained from all patients according to the regulatory and legal country-specific requirements of the participating site before enrolment in this study.

Patients who were scheduled to receive avapritinib prior to enrolment will initiate treatment after enrolment in this study based on the locally approved product label prescribing information. If a patient was already receiving avapritinib prior to enrolment, they will continue treatment at the same dose after enrolment. The dose level may be adjusted based on the locally approved product label prescribing information. Investigators must refer to the local prescribing information for contraindications, warnings and precautions as well as use in specific populations. As this study is observational, the decision to treat patients with avapritinib will be independent from the decision to enrol patients into the study.

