9.2. Setting

9.2.1. Inclusion criteria

A patient who meets all of the following criteria is eligible for inclusion:

- Written informed consent.
- Male or female, ≥ 18 years of age at the start of avapritinib treatment
- Histologically or cytologically-confirmed diagnosis of unresectable or metastatic GIST harbouring the D842V mutation in the PDGFRA gene
- Is scheduled to receive, previously received, or currently receiving first-line treatment with avapritinib consistent with the approved labelling for unresectable or metastatic GIST. Note: Patients who were treated with imatinib for ≤4 months prior to initiation of avapritinib treatment are also eligible.
- For patients who received avapritinib treatment and discontinued prior to enrolment in this study, their retrospective data must be available
- No concomitant treatment with other anticancer therapy

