9.3. Variables

The data collection plan is outlined in Table 1. Data will be collected prospectively for patients who initiate or continue to receive treatment with avapritinib. Retrospective data collection will be performed when available. All efforts will be made to ensure that the retrospective data of

patients who discontinued avapritinib treatment previously are of good quality and provide sufficient information on the variables required.

Data of interest include the following:

Demographic data and relevant medical history at the time of the first avapritinib dose:

- Age
- Sex
- Height
- Weight
- Race/ethnicity (in accordance with the local regulations)
- ECOG performance status GIST diagnosis (before the first avapritinib dose according to local standard procedures)
 - Date of diagnosis
 - Primary tumor site (e.g. stomach, duodenum, rectum, small intestine)
 - Largest lesion size ($\leq 10 \text{ cm or} > 10 \text{ cm}$)
 - Resectable (yes / no)
 - PDGFRA mutation status
 - Metastatic (yes / no)
 - Location of metastatic site(s)
- Relevant medical and surgical history including comorbidities and previous cancer diagnoses
- Prior imatinib therapy (yes / no)
- Duration of prior imatinib therapy
- Best response to prior imatinib therapy (CR, PR, SD, progressive disease, NE)
- Concomitant medications, with a special focus on CYP3A4 inhibitors/inducers to address the drug-drug interaction risk

The Medical Dictionary for Regulatory Activities (MedDRA) will be used for coding concomitant diseases, and the World Health Organization (WHO) Drug Dictionary for medications.

Avapritinib treatment details from the time of the first dose until 30 days after the last dose:

- Date of treatment initiation
- Primary reason for treatment initiation
- Setting (e.g. trial, CUP, EAP or routine care)
- Treatment schedule (e.g. qd, bid)

- Avapritinib treatment information: dose and dose modifications including date(s)
- Reason for dose modification
- Date of discontinuation or interruption
- Primary reason for discontinuation or interruption
- Reason for initiating further lines of treatment

Efficacy variables:

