9.9. Limitations of the Research Methods

9.9.1. Selection Bias

For patients who will be newly enrolled into this study, inviting consecutive patients at each site will reduce selection bias. In addition, AE rates obtained from this study will be compared with expected rates from the pooled analysis of AEs for all lines from the BLU-285-1101 and BLU-285-1303 trials. Survivor bias will be avoided (i.e. outcome ascertainment only for those who make it to the start of this study) by including patients who discontinued avapritinib treatment before enrolment in this study.

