9.9.3. Effect modifiers

Effect modification occurs when the effects of a treatment vary by presence/level of another factor (effect modifier). Stratified outcome analyses or analyses restricted to a selection of the study population will be conducted when deemed necessary and feasible, such as when population characteristics and results differ greatly between patients receiving their first dose in a controlled trial setting (i.e. enrolled in BLU-285-1101), a semi-real world setting (i.e. enrolled in a CUP or EAP and likely unable or ineligible to participate in BLU-285-1101) or real-world setting (i.e. receiving commercially available avapritinib as part of routine clinical care).

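### The concurrent-trial exclusion in 9.2.2 has no reference period, so read literally it bars discontinued patients now in a next-line trial and weakens the bias protection claimed in 9.9.1

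*Protocol*

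**What the plan says.** Section 9.1 plans three groups. The third is patients "who previously received treatment with avapritinib in the first line or following ≤4 months of imatinib treatment and have discontinued treatment". The only entry condition in 9.2.1 written for this group is: "For patients who received avapritinib treatment and discontinued prior to enrolment in this study, their retrospective data must be available".

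Two further criteria apply to everyone:

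- 9.2.1, inclusion: "No concomitant treatment with other anticancer therapy".
- 9.2.2, the sole exclusion: "Concurrent enrolment in an interventional clinical trial involving either an investigational medicinal product or medical device".

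On bias, 9.9.1 states without qualification: "Survivor bias will be avoided". The means given is "by including patients who discontinued avapritinib treatment before enrolment in this study".

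Earlier trial treatment is clearly expected among enrolled patients. Section 9.3 records the setting of avapritinib treatment, with a trial as one example. Section 9.7.2 names BLU-285-1101 as one of the settings at first dose by which results may be stratified.

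**The concern.** The discontinued group is there so that the study does not describe only patients who are still doing well on avapritinib. For that to work, entry must not depend on what happened to the patient after stopping. The 9.2.2 exclusion makes it depend on exactly that. A patient who progressed on, or could not tolerate, first-line avapritinib and then entered a trial of another agent is alive, can consent and has records on file, but is ineligible as the criterion is written.

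The situation is realistic. Section 9.2.4 directs recruitment to investigators from earlier GIST trials and clinicians with GIST trial expertise. Section 7.1 reports response rates of only 0-12% to conventional TKIs in first-line D842V-mutant disease. A further trial is therefore a plausible next step at these sites.

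AE-related discontinuation belongs to the primary objective (8.1), and duration of treatment, PFS and OS are secondary (8.2). All are estimated in whoever gets past the entry criteria, and the SAP cannot recover patients who were never enrolled.

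**Working it through.** **1. Which criteria are anchored in time.**

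| Criterion | Time reference |
|---|---|
| Age (9.2.1) | Start of avapritinib |
| Data availability (9.2.1) | Avapritinib stopped before enrolment |
| Other anticancer therapy (9.2.1) | None written; avapritinib is the implied reference drug |
| Interventional trial (9.2.2) | None written; no reference drug |

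Since 9.2.2 does not mention avapritinib, the plain reading is enrolment in another trial at the time of enrolment in this one.

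**2. Two patients with the same history.** Both take first-line avapritinib, stop, and join a next-line trial. Patient A was enrolled here while on avapritinib and meets 9.2.2 at entry. Patient B is approached after joining the trial and does not. Their avapritinib records are equally informative.

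**3. What the exclusion protects.** Under 9.7.2 the safety period ends no later than 30 days after the last avapritinib dose, and the efficacy period ends when second-line treatment starts. After that only survival is followed. For Patient B almost all the useful data predate the later trial, and for survival B is in the same position as A.

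**4. Whether another provision lets Patient B in.** Section 9.7.1.2 limits the Safety Population, the primary set for both safety and efficacy, to patients who met the eligibility criteria. The route through the ethics committee in 10.1 and the footnote to Table 1 deals with consent that cannot be obtained. It does not waive eligibility.

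**5. Size.** The protocol gives no figure on this point. Its one calculation (31 patients, 9.5) concerns ORR and has no bearing here. The protocol does not say how many patients will have discontinued or how many of those will be in a trial, so what follows is illustration on assumed values.

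Let d be the true share who discontinued for any reason and f the share of those who are barred. The observed share is d(1-f) / [d(1-f) + (1-d)]. Assume d = 40% (20 of 50):

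- f = 10% (2 patients): 0.36/0.96 = 37.5%
- f = 25% (5 patients): 0.30/0.90 = 33.3%
- f = 50% (10 patients): 0.20/0.80 = 25.0%

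Discontinuation from any cause is always understated. Everyone removed has an ended treatment duration, and those who stopped for progression also have a PFS event. This is why both endpoints would tend to look better than they are.

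**6. AE-related discontinuation has no fixed sign.** Take 21% (12/56 in 7.1) of 50 = 10.5 patients, among the same assumed 20 who discontinued.

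| Barred | Barred in proportion to all discontinuers | All barred are progressors |
|---|---|---|
| 4 | 10.5 × 0.8 / 46 = 18.3% | 10.5 / 46 = 22.8% |
| 6 | 10.5 × 0.7 / 44 = 16.7% | 10.5 / 44 = 23.9% |

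Against a true 21%, the estimate can move either way. The 12/56 is itself only an anchor: 45 of those 56 patients were treated beyond first line.

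**7. OS.** Patients barred this way are alive when approached, but have stopped first-line treatment. These features pull in opposite directions, so no sign can be given.

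**The case against.** Four arguments limit the point, and much of each stands.

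- **The anticancer-therapy criterion.** A reader might infer that it also bars patients on routine next-line treatment. The protocol does not support that. Concomitant and other need a reference drug, and the only candidate is avapritinib. Section 9.3 collects the reason for starting further lines, and 9.7.2 ends the efficacy period at second line, so later therapy is foreseen. The wording could be clearer, but it is not a bar.
- **BLU-285-1101.** A reader might infer that 9.2.2 contradicts the use of that trial as a stratum. The stratum is defined by setting at first dose, so a patient dosed there who has since left the trial is eligible. A conflict would arise only for patients still enrolled, and the protocol does not say whether the trial remains open.
- **Survivor bias.** Section 9.9.1 means by this that outcomes are ascertained only in those who reach the start of the study. A patient in a next-line trial has reached it, so losing that patient is strictly selection bias. That corrects the label. It does not change the fact that the remedy in 9.9.1 is inclusion of discontinued patients and that 9.2.2 removes some of them.
- **Extent.** Discontinued patients who are off therapy or on routine next-line care can still enter. It would be wrong to say that the protection is undone.

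A sensible site might also read 9.2.2 as referring to the avapritinib period. Others may read it literally, and different readings across sites would be a selection problem of their own.

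**Conclusion.** The point holds for the 9.2.2 exclusion. Followed as written, it removes from the planned discontinued group those who are in an interventional trial when approached, while a patient with the same history enrolled earlier stays in. The loss is confined to patients who stopped first-line avapritinib. It would tend to lengthen apparent duration of treatment and PFS. The direction for AE-discontinuation rates and OS is uncertain.

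The size is unknown. The illustrative shift from 40% to between 37.5% and 25.0% in any-cause discontinuation rests wholly on the assumed 20 of 50 discontinued and on 10% to 50% of them being barred. The protection in 9.9.1 is weakened rather than removed, but its unqualified wording claims more than the entry criteria deliver. The change should be made: it is cheap, it can only be made in the protocol, and it widens eligibility in a population the protocol calls ultra-rare.

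**What to change.** 1. In 9.2.2, and the matching text in the abstract, restrict the exclusion to enrolment in an interventional trial during the avapritinib treatment period. State that trial participation after avapritinib has been discontinued does not exclude a patient.
2. State that having received avapritinib in BLU-285-1101 is not itself an exclusion. This must accompany item 1: that trial is interventional and its avapritinib was given within it, so item 1 alone could be read as barring these patients.
3. For clarity, word the 9.2.1 criterion as no other anticancer therapy concomitant with avapritinib.
4. In 9.9.1, say that survivor bias will be reduced rather than avoided.

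The cost is a few lines of eligibility wording in a protocol amendment. No new data items are needed: 9.3 already collects treatment setting, discontinuation and the reason for further lines.

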9.2.3. Study duration

The estimated enrolment period is approximately 3 years.

It is planned to follow patients for at least 24 months for efficacy and safety events, though this may be extended based on new insights during the study period. OS is an exception and will be ascertained for all patients until study closure, which will occur when the last patient enrolled has been followed for at least 24 months or withdraws from the study for any reason.

The total study duration will therefore be the estimated 3-year enrolment period plus at least 24 months follow-up, so at least 5 years.

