Data analysis	 Analysis populations: Two analysis populations will be defined: Enrolled Population (EP) - All patients who signed informed consent Safety Population (SP) - All patients enrolled in the study who met the eligibility criteria and received at least one dose of avapritinib. The SP will be the primary analysis population for the efficacy and safety analyses. Statistical Methods: Continuous variables will be described (distribution) by their mean, standard deviation, median, extreme values (minimum and maximum) and the number of missing data. Categorical variables will be described using frequency counts and percentages. Time-to-event data will be summarized by Kaplan-Meier (KM) estimates. Data analysis: The following analyses will be performed for the primary endpoint: Number, proportions and incidence rate of patients experiencing an AE during the study period (i.e., from the first dose of avapritinib until the end of follow-up): by SOC (System Organ Class) and PT (Preferred Term) terms (MedDRA classification), severity, seriousness and relationship to avapritinib, including the description of types, severity and rates of AEs leading to discontinuation or decreased dosing of avapritinib. Number and proportions of patients with dose reductions or interruptions, or discontinuing avapritinib treatment due to an AE during the study period: overall and by comorbidity, including the description of types, severity and rates of AEs leading to discontinuation or decreased dosing of avapritinib. Number and proportions of patients with dose reductions or interruptions, or discontinuing avapritinib treatment due to an AE during the study period: overall and by comorbidity, including the description of types, severity and rates of AEs leading to discontinuation or decreased dosing of avapritinib. Ne following analyses will be performed for the secondary endpoints: OS, PFS, DOR and DoT during t

	 ORR during the study period with 95% CI based on the exact binomial distribution An interim analysis is planned for an interim study report (data lock point in November 2025, submission interim report in February 2025). Details of the interim analysis will be described in the Statistical Analysis Plan (SAP).
Milestones	This study is projected to begin enrolment in Q4 2022 and the study will end in August 2026. An interim study report is planned to be completed in February 2025 and the final study report in Q1 2027.

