6. MILESTONES

Milestone	Planned Date	
Start of data collection	By Q4 2022	
End of data collection	August 2026	
Study progress report 1	August 2022	
Study progress report 2	August 2023	
Study progress report 3	August 2024	
Study progress report 4	August 2025	
Interim report 1	February 2025	
Final report of study results	By Q1 2027	

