Baseline and follow-up assessments will be in accordance with local standard medical care. Both prospective and retrospective data collection will be performed in this study. All patients who will initiate or continue treatment with avapritinib after enrolment will have prospective data collection for 24 months on the study. For patients who have received avapritinib prior to enrolment in this study, retrospective data may also be collected (if data are available). Retrospective data collection will be performed at the participating investigator site through extraction of available data from the patient's medical records. The data collection plan is provided in Table 1.

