9.4. Data Sources

For patients who initiate or continue to receive avapritinib in this study, data will be collected prospectively for 24 months following enrolment. For patients who have already received avapritinib prior to enrolment, retrospective data will also be collected (if available). Retrospective data collection will be performed at the participating investigator site through extraction of available data from the patient's medical records as per local law and regulations. Data will include: relevant baseline data at the time of the first dose of avapritinib and safety data from the time of the first dose of avapritinib to the end of follow-up, i.e. at least 24 months, until study discontinuation for any reason, or 30 days after the last dose of avapritinib; whichever comes first. In addition, data will include efficacy data (i.e. treatment response) between the first dose of avapritinib and the end of follow-up, i.e. at least 24 months, until initiation of second-line treatment or until study discontinuation for any reason; whichever comes first (see Table 1). Survival is an exception and will be ascertained for all patients until study closure, which will

occur when the last patient enrolled has been followed for at least 24 months, or withdraws from the study for any reason.

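### Three years of enrolment from Q4 2022 plus 24 months of follow-up (60 months) does not fit an August 2026 end of data collection (43–47 months), and the protocol does not say which governs

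*Protocol*

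**What the plan says.** On duration, Protocol section 9.2.3 gives the enrolment length ("The estimated enrolment period is approximately 3 years"), the minimum follow-up ("It is planned to follow patients for at least 24 months for efficacy and safety events") and the total ("The total study duration will therefore be the estimated 3-year enrolment period plus at least 24 months follow-up, so at least 5 years"). The study design part of the abstract (section 4) repeats the 5-year estimate. Section 9.2.3 also defines when the study closes: "which will occur when the last patient enrolled has been followed for at least 24 months or withdraws from the study for any reason"; sections 9.3, 9.4 and 9.7.2 repeat that rule.

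On who must be followed, section 9.1 says: "All patients who will initiate or continue treatment with avapritinib after enrolment will have prospective data collection for 24 months on the study". Section 9.4 words it as "data will be collected prospectively for 24 months following enrolment". Patients who stopped avapritinib before enrolment contribute retrospective data and are not covered by this requirement.

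On calendar dates, the abstract says: "This study is projected to begin enrolment in Q4 2022 and the study will end in August 2026". The section 6 table has data collection starting by Q4 2022, dates the row "End of data collection" to August 2026, and puts the final report by Q1 2027.

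**The concern.** Closure is defined by patient follow-up in one part of the protocol and by a calendar date in another, and the two give different end dates. The start is now Q4 2022. Three years of enrolment followed by 24 months would end in Q4 2027, while the milestones stop data collection in August 2026.

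The study exists to meet a Specific Obligation of the conditional marketing authorisation (sections 7.2 and 8.1). Section 7.1 explains that long-term safety data in first-line patients are limited and that this matters because these patients are exposed for longer. The length of follow-up is therefore central to what the study is meant to deliver. One of two commitments must give way: 24 months of prospective data for every patient who starts or continues treatment, or the date of the final report. A SAP is not the place to settle this, because enrolment length, closure and regulatory milestones are protocol content.

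**Working it through.** **Inputs.**
- Enrolment start: Q4 2022, taken as 1 October to 31 December 2022 (sections 4 and 6).
- End of data collection: August 2026, taken as 1 to 31 August (sections 4 and 6).
- Enrolment about 36 months, minimum follow-up 24 months (section 9.2.3).
- Planned size: at least 50 (section 9.5).
- Final report: by Q1 2027 (section 6).
- Accrual pattern, and share of patients already off treatment at enrolment: not stated, so treated as assumptions below.

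**1. The plan's own total.** 36 + 24 = 60 months = 5 years. The figure in section 9.2.3 reproduces.

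**2. Calendar time available.**
- Longest: 1 October 2022 to 31 August 2026 = 47 months.
- Shortest: 31 December 2022 to 1 August 2026 = 43 months.
- Shortfall: 60 − 47 = 13 to 60 − 43 = 17 months.

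To fit 60 months before August 2026, enrolment would have had to start in August 2021. The amendment log suggests how this arose: the Version 2.0 plan began in August 2021, exactly 60 months before August 2026, and Version 3.0 moved the start to Q4 2022. The finding does not rest on that history; the current text conflicts on its own.

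**3. If August 2026 governs.**
- Last enrolment date that still allows 24 months: August 2026 − 24 months = August 2024.
- Enrolment window that fits: 43 − 24 = 19 to 47 − 24 = 23 months, against 36 stated.
- Follow-up of a patient enrolled at month 36: 43 − 36 = 7 to 47 − 36 = 11 months.
- Share of prospectively followed patients enrolled too late, assuming uniform accrual over 36 months: 1 − 23/36 = 36% to 1 − 19/36 = 47%. If all 50 patients were prospectively followed, that would be about 18–24.

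Sensitivity to accrual shape, with cumulative accrual assumed to be (t/36)^k:

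| Accrual | 23-month window | 19-month window |
|---|---|---|
| Front-loaded, k = 0.5 | 20% | 27% |
| Uniform, k = 1 | 36% | 47% |
| Back-loaded, k = 2 | 59% | 72% |

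Sensitivity to patients outside the requirement, as a share of all patients under uniform accrual, assuming a fraction r had stopped before enrolment: r = 25% gives 0.75 × (36% to 47%) = 27–35%; r = 52% gives 0.48 × (36% to 47%) = 17–23%. Both values of r are illustrative.

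**4. If the closure rule governs.**
- End of data collection: Q4 2022 + 60 months = Q4 2027.
- This is 6 months (31 March to 1 October 2027) to 12 months (1 January to 31 December 2027) after the Q1 2027 report date.
- If the present interval from end of data collection to report is kept, the report moves by the same amount as the end date, 13–17 months.

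**The case against.** The strongest defence is that these are planning dates, described as planned, estimated, approximate or projected, and that the closure rule would extend the study instead of truncating anyone. Part of this stands: under the closure rule no patient loses follow-up. But rounding around three years cannot absorb 13–17 months, since August 2026 leaves only 19–23 months for enrolment, and nothing says the closure rule overrides the milestone. Closure also allows for the last enrolled patient withdrawing, but a plan cannot count on that, and patients enrolled shortly before would still need their 24 months.

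A reader might infer more than the documents support, in three ways.

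- *That about 40% of all patients will miss the minimum follow-up.* This needs uniform accrual, a hard stop in August 2026 and a 24-month post-enrolment requirement for everyone. The first is not stated, the second is one of two competing rules, and the third contradicts sections 9.1 and 9.4, which limit the requirement to patients who start or continue avapritinib. Two of the three populations in section 9.1 are already on, or already off, treatment, so front-loaded accrual is plausible.
- *That falling short of 24 months after enrolment means falling short of 24 months of analysed data.* Section 9.7.2 starts the safety and efficacy periods at first dose. They can also end early, at 30 days after last dose for safety or at second-line treatment for efficacy. A patient already treated for a year at enrolment could have 24 months from first dose despite enrolling after August 2024.
- *That the final report is necessarily more than a year late.* Q4 2027 is 6–12 months after Q1 2027; the longer delay follows only if the current reporting interval is kept. Section 12 separately allows up to one year after completion, so it is the section 6 date that fails.

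It is also fair that the planned estimators, incidence per person-month and Kaplan–Meier, accommodate unequal follow-up. Truncation would cost long-term information; it would not by itself invalidate the analyses.

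**Conclusion.** The contradiction is real under every reading of the stated dates: 60 months are required, 43–47 are available, and the shortfall is 13–17 months. No other section resolves it.

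The consequence depends on which rule is followed:
- **August 2026 kept:** patients who start or continue avapritinib and enrol after August 2024 cannot have 24 months of prospective data. Under an assumed uniform 36-month accrual this is roughly 36–47% of prospectively followed patients (20–27% front-loaded, 59–72% back-loaded), and a smaller share of all patients to the extent that some had stopped before enrolment.
- **Closure rule kept:** nobody is cut off. Data collection ends about Q4 2027, and the report slips about 13–17 months if the present interval is preserved.

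The date conflict rests on no assumption; only the percentages and the size of the report delay do. It needs correcting in the protocol because the stated follow-up and the report date cannot both be honoured as planned.

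**What to change.** Reconcile sections 4, 6, 9.2.3 and 12 in one of two ways, and state explicitly which rule governs if follow-up and calendar date diverge.

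- **Follow-up governs.** Set end of data collection to last patient in plus 24 months, about Q4 2027 for a three-year enrolment, and move the final report to match. Cost: a later final report to the regulator.
- **Date governs.** Keep August 2026, state that enrolment of prospectively followed patients closes by August 2024, and restate the enrolment period (about 19–23 months) and the total duration (under 4 years). Cost: a shorter window in which to recruit at least 50 patients in an ultra-rare population.

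Either way the change is a protocol amendment of dates, notified to the regulator; no analysis method changes.
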